## **Study Protocol**

The purpose of the proposed study is to conduct a study on individuals with lower limb amputation evaluating if residual limb fluid volume data collected using a novel non-invasive device is beneficial towards prosthetic prescription, fit, and comfort as determined by amputee test subjects and practitioners (prosthetists). Residual limb volume/mass changes typically affect prosthetic limb fit of people with limb amputation, and changes in limb volume/mass can put the limb at risk of injury and preclude use of the prosthesis.

Participants' residual limb fluid volume will be monitored through segmental bioimpedance analysis both before and after a practitioner-issued modification to the prosthesis as an observational cohort study and a blinded randomized clinical trial in which the data may or may not be shared with the practitioner before the modification is made to the prosthesis.

The Specific Aims are to:

[figure not shown]
Aim 1. Characterize residual limb volume accommodation strategies and associated clinical outcomes experienced by prosthetic users with different activity/volume profiles. Changes in users' limb volume, prosthetic fit, performance, and satisfaction will be used to determine which strategies are most predictive of positive clinical outcomes. This aim will be accomplished using an Observational Cohort Study.

Aim 2. Compare the effectiveness of bioimpedance-enhanced and traditional prosthetic evaluation, design, and fitting practices for lower limb participants who require adjustment or replacement of their volume management system. Differences in participants' limb volume, prosthetic fit, performance, and satisfaction will be used to assess if bioimpedance-enhanced fitting produces superior outcomes compared to traditional, experience-based fitting methods. This aim will be accomplished by using a Randomized Controlled Trial (RCT).

[figure not shown]
Primary quantitative data will be collected via custom study instruments, such as a bioimpedance measurement system to assess limb volume changes. Qualitative data will be collected from participants directly through self-report of their health history, during study procedures. All data for this research will be collected prospectively.

A more detailed timeline of the study procedures is given on the following pages.

# Aim 1

## Aim 2

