### **Aim 2**

Data collected at each assessment (i.e., pre-implementation, 1-month follow-up, and 6-month follow-up) in Aim 2 will be visually analyzed using histograms and boxplots. Next, we will test data for normality using a Shapiro-Wilk test. If the data is found to be normally distributed, our hypothesis will be evaluated using clinical outcome measure scores (e.g., SCS) in a repeated-measures analysis of variance (rmANOVA) to assess differences in outcomes achieved by participants assigned to the treatment (i.e., bioimpedance-enhanced fitting) group vs. control (i.e., traditional fitting) group over time. In the event that data are not normally distributed, we will use a nonparametric Friedman test to assess differences in outcomes between bioimpedance-enhance and traditional fitting. Significance for statistical tests will be set at  $\alpha < 0.05$ . Our hypothesis will be evaluated using outcome variables of number of visits and total visit time. We will compare the total number of visits and total time over the 6-month period between the treatment and control groups using a t-test for independent samples.

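### On the Aim 2 scores, the Friedman branch cannot compare the randomised arms, and the rmANOVA names neither the effect that tests superiority nor a baseline covariate

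*Combined protocol and SAP*

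**What the plan says.** The Study Protocol sets Aim 2 as a randomised trial whose results "will be used to assess if bioimpedance-enhanced fitting produces superior outcomes compared to traditional, experience-based fitting methods".

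The Aim 2 section of the Statistical Analysis Plan starts from "Data collected at each assessment (i.e., pre-implementation, 1-month follow-up, and 6-month follow-up) in Aim 2", so a pre-implementation score is collected. After a Shapiro-Wilk test there are two branches.

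- **Normal data:** "our hypothesis will be evaluated using clinical outcome measure scores (e.g., SCS"), and this is done "in a repeated-measures analysis of variance (rmANOVA) to assess differences in outcomes achieved by participants assigned to the treatment" (bioimpedance-enhanced) "group vs. control (i.e., traditional fitting) group over time". No main effect, interaction or single-visit contrast is named as the test, and no covariate is listed.
- **Non-normal data:** "In the event that data are not normally distributed, we will use a nonparametric Friedman test to assess differences in outcomes" between the two fitting methods.

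SCS, the socket comfort score, appears there only as an example. The Aim 1 section calls it the primary outcome measure, but for Aim 1. Number of visits and total visit time have their own named test, an independent-samples t-test.

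**The concern.** There are three gaps, in order of firmness.

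1. **The Friedman branch does not test the hypothesis.** It asks whether scores differ across visits within participants. The aim asks whether the arms differ. A significant result could mean only that both arms changed after the socket was modified.
2. **The rmANOVA effect is open.** The arm main effect and the arm-by-time interaction answer different questions and can differ widely in power. If neither is named, the choice can be made after the data are seen. The interaction over three occasions has 2 degrees of freedom and gives no single estimate of benefit.
3. **The baseline score is not used as a covariate.** It is already collected, and in a randomised comparison adjusting for it is usually the more precise way to estimate a given contrast.

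**Working it through.** **Inputs.** From the SAP, Aim 2: three occasions, two arms and a 0.05 significance level (two-sided assumed, since sidedness is not stated). The documents give no Aim 2 sample size, SD, effect or correlation, so there is no planned figure to reproduce. Assumed: unit variance at each visit, equal correlation rho between any two visits, equal arms and complete data. That the pre-implementation score is a level of the time factor is inferred from the wording.

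**1. Friedman branch.** Each participant's three scores are replaced by ranks 1 to 3, and the statistic compares rank sums across visits. Arm enters nowhere. Running the test separately by arm gives two within-arm p-values, and comparing those is not a test of the arm difference. As an illustration, take no arm difference, both arms improving by an assumed 0.7 SD at both follow-ups, rho 0.5 and 15 to 40 per arm. The Friedman test on the pooled arms rejected in 91 to 100% of simulated trials, although the treatment had no effect relative to control.

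**2. Same contrast, change score against baseline adjustment.** Variances are per participant.

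| Contrast | Quantity | rho 0.3 | rho 0.5 | rho 0.7 |
|---|---|---|---|---|
| One visit | Change, 2(1 - rho) | 1.40 | 1.00 | 0.60 |
| One visit | Adjusted, 1 - rho² | 0.91 | 0.75 | 0.51 |
| One visit | Ratio, (1 + rho)/2 | 0.65 | 0.75 | 0.85 |
| Follow-up average | Change, 1.5(1 - rho) | 1.05 | 0.75 | 0.45 |
| Follow-up average | Adjusted, (1 - rho)(1 + 2rho)/2 | 0.56 | 0.50 | 0.36 |
| Follow-up average | Ratio, (1 + 2rho)/3 | 0.53 | 0.67 | 0.80 |

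At one visit the inverse ratio, 2/(1 + rho), is 1.54, 1.33 and 1.18. The change score therefore needs 54, 33 and 18% more participants for the same precision.

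**3. Small arms.** Estimating the baseline slope multiplies the adjusted variance by about 1 + 1/(2n - 4), with n per arm. At n = 10 and rho = 0.9 the one-visit ratio is 0.95 × (1 + 1/16) = 0.95 × 1.0625 = 1.01 (1.02 by simulation), so the gain is gone. At n = 20 and rho = 0.5 it is 0.75 × (1 + 1/36) = 0.77.

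**4. Main-effect reading.** With baseline as one of three response levels and a constant effect d at both follow-ups, the arm main effect estimates (0 + d + d)/3 = 2d/3.

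**5. Power when the 2-df interaction has 80%.** Large-sample noncentral chi-square, noncentrality 9.635 fixed within each effect pattern, same number of participants.

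| Test | Effect pattern | rho 0.3 | rho 0.5 | rho 0.7 |
|---|---|---|---|---|
| Arm main effect | constant | 83% | 59% | 34% |
| Adjusted 6-month | constant, or 6 months only | 92% | 87% | 83% |
| Adjusted 6-month | halves by 6 months | 49% | 43% | 39% |
| Adjusted 6-month | gone by 6 months | 5% | 5% | 5% |
| Adjusted average | constant | 99% | 97% | 93% |
| Adjusted average | one visit only | 57% | 48% | 41% |

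**6. Whether a normality switch is needed.** With exactly normal data and an assumed 15 to 40 per arm, at least one of three pooled Shapiro-Wilk tests rejected in 12.5 to 15.6% of simulated trials. With null data that were lognormal, or rounded to an assumed 0 to 10 scale with a ceiling (rho 0.5), at least one rejected in 91 to 100%. In those non-normal settings the type I error of the adjusted 6-month and averaged contrasts (ANCOVA form, complete data) was 4.4 to 5.8%.

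**The case against.** The strongest reply is that the main branch is sound. The wording about differences over time points to the arm-by-time interaction. Under that reading nothing is diluted, baseline is used, and the test is valid with complete data if sphericity holds or is corrected for. Baseline adjustment is then an efficiency preference whose size cannot be fixed from these documents. This stands, and it limits the covariate part of the point.

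A reader might infer three stronger things that the documents do not support.

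- **That the plan dilutes the treatment effect.** The two-thirds figure applies only if the arm main effect including baseline is the test, and the SAP does not say so.
- **That a real benefit is bound to be easier to miss as planned.** The precision loss holds for the same contrast. Replacing a 2-df test by a single contrast also changes the contrast, and which test then has more power depends on an effect pattern that is not known.
- **That change scores are always noisier.** In very small arms with rho near 0.9 they are not.

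Two further limits apply. Equal correlation is a simplification for visits at 1 and 6 months. Timeline figures are missing from the extracted text, so timing or outcome details may have stood there. Neither limit rescues the Friedman branch, whose lack of an arm term needs no assumption.

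**Conclusion.** The point holds in three parts of unequal strength. The Friedman branch gives no between-arm comparison and cannot answer the Aim 2 question; this follows from the test itself. The rmANOVA designates no effect; this is plain from the text, and under the stated assumptions the choice can move power by tens of percentage points. At rho 0.7 with a constant effect, for example, the main effect has 34% where the interaction has 80%. The absent baseline covariate costs precision, not validity: for the same one-visit contrast the adjusted variance is 0.65 to 0.85 of the change-score variance for rho 0.3 to 0.7, and the gain shrinks as rho rises. If only the two follow-ups were modelled, their unadjusted average would have variance (1 + rho)/2 = 0.65, 0.75, 0.85 against 0.56, 0.50, 0.36 adjusted, so adjustment would help there too. All these magnitudes are illustrative. The t-tests on visit count and visit time are unaffected. The change should be made; the main branch is not invalid without it.

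**What to change.** - **Model.** Analyse each Aim 2 clinical score at 1 and 6 months in a mixed model with arm, visit, arm-by-visit, baseline score and baseline-by-visit, including all randomised participants with any follow-up score.
- **Test.** Before unblinding, prespecify which baseline-adjusted arm contrast is the test: a named visit or the average of the two follow-ups. Report it with a 95% CI, together with the adjusted difference at each visit.
- **Normality.** Use that contrast whatever the Shapiro-Wilk result. Replace the Friedman branch with a robust or rank-based between-arm comparison adjusted for baseline, as a sensitivity analysis.

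**Cost.** SAP wording, slightly more analysis and about one degree of freedom; no new data. The real trade-off is the choice of contrast. The average has less power than the 2-df interaction if the effect is at one visit only, and a 6-month contrast has less if the effect fades. The sponsor should choose by the pattern it expects. Participants with no follow-up score still drop out of the analysis.

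### For the Aim 2 clinical scores, rmANOVA and its Friedman fallback by default use only participants with all three scores, and no stated rule keeps partial data

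*Combined protocol and SAP*

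**What the plan says.** The Study Protocol makes Aim 2 a randomised comparison of bioimpedance-enhanced with traditional fitting. The Aim 2 section of the SAP starts from "Data collected at each assessment (i.e., pre-implementation, 1-month follow-up, and 6-month follow-up) in Aim 2", which is plotted and then tested for normality by Shapiro-Wilk. If normality is accepted, the clinical scores are evaluated "in a repeated-measures analysis of variance (rmANOVA) to assess differences in outcomes achieved by participants assigned to the treatment" or control group over time. If it is not, "we will use a nonparametric Friedman test to assess differences in outcomes between bioimpedance-enhance and traditional fitting".

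The documents name no analysis population, no rule for withdrawals or missed visits, no imputation, no mixed or likelihood-based model and no sensitivity analysis. They give no sample size, standard deviation, effect size or retention figure for Aim 2.

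This point covers only the repeated clinical scores. The number of visits and total visit time are compared by an independent-samples t-test and are not considered here.

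**The concern.** The sentence describes a comparison of participants as assigned, but the methods it names work on complete sets of three scores. Someone who attends before the modification and at 1 month, then leaves, would lose the 1-month score already recorded. Someone who misses only the 1-month visit would lose the 6-month score. The Friedman branch offers no escape, because it too needs complete blocks.

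Two things are at stake. One is precision: collected follow-up data are thrown away whatever the reason for the gap. The other is the protection given by randomisation: if the chance of a gap is related to the scores and differs by arm, the completers in the two arms are no longer comparable.

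**Working it through.** **Inputs.** Three assessments, two of them follow-ups, and the two named tests come from the SAP, Aim 2. The plan has no Aim 2 sample size, power or dropout figure to reproduce, so every rate below is an assumption. Let q be the proportion missing each follow-up, independently between visits, with the first assessment complete.

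**1. Default behaviour.** A standard repeated-measures ANOVA routine was given 10 invented participants with three visits each and one score removed. It refused the data as unbalanced. The analyst must then delete that person or fill in the score, and the plan provides for no filling in.

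**2. Participants deleted and precision lost.** The share deleted is 1 − (1 − q)². At 1 month, a model using all observed scores has a share 1 − q of participants, and the completers' analysis has (1 − q)². The ratio of interval widths is √[(1 − q)/(1 − q)²] = 1/√(1 − q). This ignores a small further gain to the model from correlation between visits.

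| q | Deleted | Width ratio at 1 month |
|---|---|---|
| 0.05 | 1 − 0.9025 = 10% | 1/√0.95 = 1.026 |
| 0.10 | 1 − 0.81 = 19% | √(0.90/0.81) = 1.054 |
| 0.15 | 1 − 0.7225 = 28% | √(0.85/0.7225) = 1.085 |
| 0.20 | 1 − 0.64 = 36% | √(0.80/0.64) = 1.118 |

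If instead 20% of participants all leave after their 1-month visit, the model keeps every 1-month score and the completers' analysis keeps 80%. The ratio is then 1/√0.80 = 1.118, about 12%. In that case the 6-month gain is only what correlation with the earlier scores supplies.

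**3. Can the contrast be biased?** An illustrative simulation used 400,000 per arm, SD 1, higher scores better, a true effect of 0 and equal correlations between visits. In the control arm, participants in the lowest 20% at 1 month missed 6 months with probability 0.6 and the rest with probability 0.10. The overall loss is 0.2 × 0.6 + 0.8 × 0.10 = 0.20. In the treatment arm 20% were lost at random. Treatment minus control, in SD units:

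| Correlation | Completers, 1 month | Completers, 6 months | Completers, change to 6 months | All observed scores, 6 months |
|---|---|---|---|---|
| 0.5 | −0.171 | −0.085 | 0.003 | 0.003 |
| 0.7 | −0.173 | −0.121 | 0.001 | 0.003 |

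The completers' difference at the first assessment is the 6-month difference minus the difference in change: −0.085 − 0.003 = −0.088, and −0.121 − 0.001 = −0.122. Their 1-month change contrast is therefore −0.171 + 0.088 = −0.083, and −0.173 + 0.122 = −0.051.

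The change to 6 months comes out near zero here because the 1-month score is equally correlated with the other two visits, so that result is not general. With the same dropout mechanism in both arms, the completers' contrasts at 1 month, at 6 months and in change to 6 months were all within 0.003 of zero. The negative sign arises because the selective dropout was placed in the control arm; placing it in the other arm reverses the sign.

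**The case against.** The strongest reply is that the plan never says incomplete participants will be excluded. A repeated-measures analysis can be fitted as a mixed model that keeps partial rows, imputation beforehand is not ruled out, and the sentence refers to participants by assignment. This stands as far as it goes: deletion is the default of the named methods and not a written rule, so a reader who infers that the plan states an exclusion goes too far. But nothing indicates that a mixed model or imputation is intended, and the Friedman test as the alternative points to the conventional complete-data version. If partial data are to be kept, the SAP needs to say how before results are seen.

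A reader might also infer that the completers' comparison understates the benefit, because badly fitted participants stop attending. The documents do not support this. They give no reasons for non-attendance. Aim 2 enrols people whose volume management already needs changing and counts visits as an outcome, so a poor fit could equally bring people back more often.

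Finally, materiality is unknown. With complete follow-up the problem disappears, and with similar dropout mechanisms in both arms the bias may be negligible. That limits how strongly the point can be pressed. It does not remove the loss of precision under any other pattern of gaps.

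**Conclusion.** The concern holds in this form: as written, the Aim 2 score comparison defaults to completers on both branches and discards follow-up scores already collected. A change is worth making because it is cheap, not because harm has been shown.

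Under assumed independent missingness of 10% or 15% per follow-up, 19% or 28% of participants are deleted and the 1-month interval is about 5% or 8% wider than it need be. A reader might pair the deletion of about 20% with a 12% wider interval. That pairing is right only if all of that 20% leave after their 1-month visit.

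Bias is possible when dropout depends on the scores and differs by arm. The simulation shows that it can occur, but its size depends on assumed correlations and mechanisms, and the documents settle neither size nor direction.

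**What to change.** For the Aim 2 clinical scores, replace both the rmANOVA and the Shapiro-Wilk/Friedman branch. Keeping that branch would send non-normal scores back to a complete-block test. The SAP should specify:

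- a likelihood-based mixed model for repeated measures with arm, visit and arm-by-visit terms and an unstructured covariance;
- the baseline score either as a covariate or as a response with the arm means constrained to be equal, with one option chosen in advance;
- small-sample degrees of freedom, such as Kenward-Roger, since the sample size is not stated;
- inclusion of every randomised participant with any follow-up score, in the assigned arm;
- a statement that a missed visit or withdrawal does not remove earlier scores;
- the completers-only analysis, reported as a sensitivity analysis.

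The cost is SAP wording and a different software procedure, with no extra visits, staff or participants. The small downside is that the model assumes dropout depends only on observed data. That is weaker than what the completers-only analysis needs, but it is still an assumption, and the completers-only sensitivity analysis does not test it. Nor does the model recover information on participants with no follow-up score at all.

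### Aim 2 clinical scores: the Friedman fallback has no between-group term, so it cannot compare the two randomised arms

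*Combined protocol and SAP*

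**What the plan says.** The Study Protocol section sets Aim 2 up as a randomised trial ("This aim will be accomplished by using a Randomized Controlled Trial (RCT") in which differences in limb volume, fit, performance and satisfaction "will be used to assess if bioimpedance-enhanced fitting produces superior outcomes compared to traditional, experience-based fitting methods".

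The Aim 2 section of the SAP has three assessments: "pre-implementation, 1-month follow-up, and 6-month follow-up". It then says "Next, we will test data for normality using a Shapiro-Wilk test". If the data pass, a repeated-measures ANOVA of the clinical scores (socket comfort score is the example) assesses "differences in outcomes achieved by participants assigned to the treatment (i.e., bioimpedance-enhanced fitting) group vs. control (i.e., traditional fitting) group over time". If they do not, "we will use a nonparametric Friedman test to assess differences in outcomes between bioimpedance-enhance and traditional fitting".

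Number of visits and total visit time are handled separately: they are compared "between the treatment and control groups using a t-test for independent samples".

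**The concern.** The normal-data branch contains the randomised contrast. The non-normal branch is described as if it did, but the named test has no place for a between-subject factor. Failing a distributional check would therefore change the question being tested as well as the method.

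Two errors could follow. Improvement common to both arms could be reported as a benefit of bioimpedance-enhanced fitting. This is a realistic risk, because everyone enrolled in Aim 2 needs a volume management system adjusted or replaced, and both arms receive a fitting. Conversely, a real difference between arms could be missed. The alternative is to choose a replacement test after seeing the data, which gives up prespecification.

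**Working it through.** **Inputs from the documents.** Two parallel arms of different people (randomised trial; independent-samples t-test for visits), three assessments, alpha 0.05. For Aim 2 there is no sample size, SD, effect size or power figure, so there is no stated figure to reproduce. The check rests on the structure of the test, followed by simulation.

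**Structure.** With *N* blocks, *k* conditions and rank sums *R_j*, the Friedman statistic is

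Q = 12 / [N k (k+1)] × Σ R_j² − 3 N (k+1).

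It can be applied to this design in three ways.

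1. *Participants as blocks, three visits as conditions, arms pooled.* The arm label does not appear in Q. In one simulated data set of 40 participants, reordering the participants, and so reassigning them to arms, left Q at 1.153 and p at 0.562. This tests change over time.
2. *The same test within each arm.* This gives two tests of time and none of arm. Significance in one arm but not the other is not a comparison of arms.
3. *Arms as conditions, three assessments as blocks, one summary value per cell.* With N = 3 and k = 2, the most extreme result has rank sums 3 and 6: Q = 12/(3×2×3) × (3² + 6²) − 3×3×3 = 30 − 27 = 3.0. The chi-square (1 df) p is 0.083 and the exact p is 2/8 = 0.25. It can never reach 0.05.

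**Simulation.** Assumptions, none from the documents: integer score clipped to 0-10, SD 2, within-person correlation 0.5, baseline mean 6, the same change at both follow-ups, 1:1 allocation, 4000 replicates per scenario (Monte Carlo standard error at most 0.8 percentage points). Rejection rates for the pooled Friedman test:

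| Scenario | 20 per arm | 30 per arm |
|---|---|---|
| Identical arms, no change | 4.6% | 4.8% |
| Identical arms, both +0.5 | 27.8% | 39.1% |
| Identical arms, both +1 | 81.4% | 94.3% |
| Arms differ by 1.5: −0.75 and +0.75 | 3.9% | 3.8% |
| Arms differ by 1.5: 0 and +1.5 | 48.8% | 67.5% |

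Rows 2 and 3 are false claims if the result is read as an arm difference. In the last row the test responds to the pooled change over time.

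Under the within-arm reading, with identical arms both gaining 1, the two tests disagree on significance in 51.6% and 43.8% of trials.

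**Comparison with a test that uses the arm.** Quade's rank analysis of covariance, adjusted for the pre-implementation score, rejects in 4-5% of the identical-arm trials. In the two 1.5-point scenarios its power is about 70% and 88% on the 6-month score, and about 86% and 96-97% on the average of the 1- and 6-month scores.

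**How often the switch would occur.** The SAP does not say which data are tested or what result triggers the switch. On exactly normal data at 20 per arm, Shapiro-Wilk rejects in 4.8% of trials (one visit, arms pooled), 13.5% (any of three visits) or 25.4% (any of six arm-by-visit tests). On rounded 0-10 scores with means of 5 to 8, the rate runs from about 25% to 100%, depending on the rule and the mean.

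**The case against.** The defect operates only if Shapiro-Wilk triggers the switch, and that frequency is unknown. The repeated-measures ANOVA branch is sound, and visits and visit time keep a valid two-sample test. No Aim 2 primary outcome is named, and the intention to compare arms is plain, so this could be called a misnamed test. These points limit the scope. They do not supply a between-arm analysis of non-normal scores, and the visit outcomes do not answer the question about fit, performance and satisfaction.

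The percentages depend on assumed inputs, and this stands. At 20 per arm with both arms gaining 1, the 81% falls to about 45% with SD 2.5 and correlation 0.3, and rises to almost 100% with SD 1.5 and correlation 0.7. The 4% case requires controls to worsen exactly as much as treated participants improve. The direction of the error, and the absence of an arm term, do not depend on these values.

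A follow-up average also narrows the question, and its power advantage needs an effect at both visits. This stands too. With the 1.5-point effect at 6 months only, power on the average falls to about 32% (20 per arm) and just under 50% (30 per arm), against about 71% and 88% on the 6-month score. The documents do not say when an effect is expected.

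Finally, the Aim 2 timeline is missing from the available text, so the absence of pairing is a statement about that text. The independent-samples t-test makes pairing unlikely.

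**Conclusion.** The concern holds and must be fixed. As written, the fallback for the Aim 2 clinical scores cannot compare bioimpedance-enhanced with traditional fitting: two of its three possible readings test time, and the third cannot reach significance at 0.05. This follows from the design and the test alone. The size of the resulting error is conditional on the simulation assumptions: up to 94% false rejection when identical arms both gain 1 point, and as little as 4% rejection for a true 1.5-point difference in the worst case. The finding is confined to the clinical scores and to the case where the switch is made.

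**What to change.** Keep the repeated-measures ANOVA and replace only the Friedman sentence with a fallback that retains the arm contrast. Two options:

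- An ordinal or robust mixed model testing arm-by-time. This stays closest to the ANOVA's question.
- A rank analysis of covariance on one follow-up summary. Possible wording: *If the normality criterion defined above is not met, the two groups will be compared by rank analysis of covariance on the average of the 1- and 6-month scores, adjusted for the pre-implementation score, at two-sided alpha 0.05.* One named visit may replace the average, but only one, so that no second test is added. The average suits a sustained effect and the 6-month score a late one. The choice should be made and justified in advance.

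State which data the Shapiro-Wilk test is applied to and what result triggers the switch. Optionally, prespecify a single baseline-adjusted between-arm model with robust standard errors whatever the distribution, which removes the need for the check.

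The cost is SAP wording only: no new data, visits or participants.

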## **Statistical Analysis Plan**

### **Aim 1**

Aim 1 is an exploratory study with the objective of generating potential volume management strategies based on the measurement of limb fluid volume fluctuations via bioimpedance. As such, it does not involve statistical hypothesis testing per se, and therefore, no power analysis is involved. The primary outcome measure of socket comfort score (SCS), pre and post socket modification will be analyzed. A Shapiro-Wilk test will be used to determine normalcy. Normally distributed data will be compared using paired t-tests. If data is not normally distributed, a Wilcoxon Signed Rank Test will be used to make comparisons. A significance level of 0.05 will be used to determine whether measured differences in limb volume were statistically significant between interventions.

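### The Aim 2 superiority hypothesis is tested on clinical scores, number of visits and total visit time at 0.05, with no primary outcome, multiplicity adjustment or success rule

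*Combined protocol and SAP*

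**What the plan says.** The Aim 2 section of the SAP ties the hypothesis to outcomes in two places.

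- Clinical scores: "our hypothesis will be evaluated using clinical outcome measure scores (e.g., SCS) in a repeated-measures analysis of variance (rmANOVA"), with a Friedman test if the data are not normal. The scores are plural, and SCS is only an example. Assessments are before implementation and at 1 and 6 months; no time point is singled out.
- Visits and time: "Our hypothesis will be evaluated using outcome variables of number of visits and total visit time". Each is to be compared between the arms over 6 months by a two-sample t-test.

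Between these two statements comes the only error control, a sentence beginning "Significance for statistical tests will be set at" and giving 0.05.

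The SAP uses the word primary once, under Aim 1: "The primary outcome measure of socket comfort score (SCS), pre and post socket modification will be analyzed". That section describes Aim 1 as exploratory.

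The Study Protocol section gives the basis for the Aim 2 conclusion as differences in "limb volume, prosthetic fit, performance, and satisfaction will be used to assess if bioimpedance-enhanced fitting produces superior outcomes". It does not mention visits or visit time.

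**The concern.** Aim 2 is a randomised trial meant to conclude whether one fitting method is superior to another. That conclusion has a known error rate only if the plan fixes in advance which test, or which combination of tests, decides it. Here the same phrase about the hypothesis is attached to an unlisted set of scores and to two further outcomes with their own between-arm tests. Nothing ranks them or says how they combine.

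Two things are at stake. If any one significant result is taken as support, the false-positive rate exceeds 5%. And because the rule is not written down, the deciding outcome could be picked once the results are known. The protocol's domain list and the SAP's outcome list also differ. SCS may fall under fit or satisfaction, but visits and visit time are additions, and limb volume is not named in the Aim 2 SAP text.

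**Working it through.** **Figure to reproduce.** None. The only Aim 2 design figure is the 0.05 level. No sample size, power or overall error rate is stated for Aim 2, so the check asks what 0.05 per test implies.

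**Inputs from the documents (SAP, Aim 2).** Level 0.05 for statistical tests; at least three outcomes (one clinical score, number of visits, total visit time).

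**Assumptions.** Tests are two-sided (sidedness is not stated). Test statistics are jointly normal with no true difference on any outcome. SCS is represented by a single between-arm contrast. The correlations are assumed because the documents give none. Signs are oriented so that positive means benefit from bioimpedance.

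**Rule A: one significant result is enough.**

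Independent outcomes:
- either direction: 1 − 0.95³ = 0.143
- favouring bioimpedance: 1 − 0.975³ = 0.073

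Correlated outcomes, the probability that at least one |Z| exceeds 1.96 (for the favourable direction, at least one Z above 1.96):

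| Visits–time r | SCS with each r | Either direction | Favouring bioimpedance |
|---|---|---|---|
| 0 | 0 | 0.143 | 0.073 |
| 0.5 | 0.2 | 0.134 | 0.068 |
| 0.7 | 0.2 | 0.128 | 0.064 |
| 0.8 | 0.2 | 0.123 | 0.062 |
| 0.9 | 0.2 | 0.116 | 0.058 |
| 0.9 | 0.5 | 0.108 | 0.054 |
| Single test | – | 0.050 | 0.025 |

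A finite-sample check with t-tests at an assumed 15 or 30 per arm and correlations (0.8, 0.2) gave 0.120–0.125 and 0.060–0.063.

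**Effect of the open score list under Rule A.** Two clinical scores (an assumed count, r 0.3 to 0.7 between them) plus visits and time (r 0.8), cross-correlation 0.2: 0.153–0.163 in either direction, 0.077–0.082 favouring bioimpedance. One test for each of the four protocol domains plus visits and time makes six tests: 1 − 0.95⁶ = 0.265 if independent, about 0.208 at a common correlation of 0.5.

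**Rule B: all three must be significant.** The rate cannot exceed 0.05. With the correlations in the table's first and last three-outcome rows it is about 0.0001 and 0.007.

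**Rule C: two separate hypotheses, clinical and efficiency.** The clinical hypothesis has a rate of 0.05 if it rests on one score. The efficiency hypothesis, if either visits or time suffices, has about 0.091 at visits–time correlation 0.5 and 0.070 at 0.9.

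**After the fix.** One named primary test has a rate of 0.05. If three co-equal outcomes were kept with Bonferroni, each at 0.05/3 = 0.0167, the rate would be 1 − (1 − 0.0167)³ = 0.049 if independent and at most 0.05 otherwise.

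**The case against.** The strongest reply is that the inflation depends on a rule the plan never states. If all three outcomes had to be significant, the error rate would be well below 5%. That is right, and it limits the claim: what is shown is an unstated decision rule, with inflation as one consequence. It does not rescue the plan, because a reader cannot tell which rule applies.

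Second, visits and time may be a separate efficiency hypothesis, which would explain why the protocol omits them from its superiority domains. The hypothesis is never written out, so this reading is possible. But the SAP uses the same words both times and does not separate the two. Even on this reading, visits plus time carry about 7% to 9% if either suffices, and the score list remains open.

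Third, the calculation treats SCS as one signed statistic, whereas the plan has a repeated-measures ANOVA over three assessments. A group-by-time F-test there has no sign. This stands as a limit on the directional figures, which should be read as approximate. It is also a reason to name a single between-arm contrast.

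Fourth, some protocol figures are not shown. The protocol describes the pages that follow as a timeline of procedures, and the Aim 2 analysis text reads as complete. Outcome labels might appear in the missing material, but the point here concerns what the SAP says.

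**Conclusion.** The concern holds. The SAP tests the Aim 2 hypothesis on at least three outcomes at 0.05, without naming a primary outcome, adjusting for multiplicity or saying what counts as success. The primary label given to SCS under Aim 1 belongs to a pre/post comparison in an exploratory study and does not fill the gap.

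If one significant result is enough, three outcomes give about 11% to 14% in either direction and 5% to 7% favouring bioimpedance, roughly two to three times the single-test rates. Further scores would raise this. These figures rest on that reading, on assumed correlations and on two-sided tests. A stricter rule would give 5% or less. The firm conclusion is that the plan as written does not guarantee a 5% error rate for its superiority claim.

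**What to change.** Before unblinded analysis, amend the Aim 2 section of the SAP as follows.

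1. Name one primary outcome and one between-arm contrast, tested at two-sided 0.05. SCS is a natural example, being the only clinical score the SAP names, either at 6 months or as the group effect over the 1- and 6-month follow-ups.
2. List the remaining scores by name and make them secondary, together with number of visits and total visit time. Use Holm adjustment, or report estimates and confidence intervals only.
3. State that superiority is concluded only if the primary test is significant and favours bioimpedance.
4. Align the Aim 2 outcome lists in the Study Protocol and the SAP. If visits and time were meant as a separate efficiency hypothesis, write it out with its own error control.

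Co-primary outcomes or a Bonferroni split would also control the error rate if the sponsor prefers them; what matters is that the rule is fixed in advance.

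The cost is wording in two documents, with no new data collection. The price is that a positive result on visits or visit time alone would no longer support the main claim. With no Aim 2 sample size or power in the documents, whether the trial is large enough for the chosen primary outcome cannot be judged from them.
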